## 9.11. Publication and Data Sharing Policy

Publication of complete data from the study is planned. It is anticipated that the results of this study will be presented at scientific meetings and/or published in a peer reviewed scientific or medical journal. A Publications Committee composed of Investigators participating in the study and representatives from RADIUS as appropriate will be formed to oversee the publication of the study results, which will reflect the experience of all participating study centers.

Subsequently, individual Investigators may publish results from the study in compliance with their agreement with RADIUS.

WHO	World Health Organization

1 BACKGROUND

This Statistical Analysis Plan (SAP) describes the statistical methods for Study BA058-05-022 to analyze usability, pharmacodynamic and safety data. The method for analyzing the pharmacokinetic data will be described in the Pharmacometric Analysis Plan (PAP) as a separate document.

1.1 Study Objectives

The primary objective of this study, as stated in Section 2 of the protocol, is to evaluate the ability of subjects to self-administer 300 µg abaloparatide-sMTS over a period of 29 days based on pharmacokinetic (PK) and pharmacodynamic (PD) markers.

1.2 Study Design

1.2.1 Synopsis of Study Design

This is an open-label study to evaluate the usability of the abaloparatide-sMTS by subjects with low BMD. The study will consist of a Screening Period (up to 2 months), a Pre-Treatment Period (1 week), a Treatment Period (1 month), and a 1 week Follow-Up after the last dose of study medication. Thus, subjects will be in the study for up to 4 months. Eligible subjects will undergo protocol specified procedures, including BMD (if dual energy x-ray absorptiometry [DXA] was done over 12 months prior to Screening) and bone turnover marker assessment. For the purpose of this study, 1 month is equivalent to 30 days.

All eligible subjects will be provided calcium and vitamin D to ensure that their daily intake is 1,200 mg/day and 800 IU/day, respectively, or a dose determined by the Investigator and agreed by the Sponsor Medical Monitor, according to the subject's need.

The study design is presented in [Figure 1](#). All subjects will undergo safety, pharmacokinetic, bone turnover marker (s-PINP), and assessments of User Errors and Subject Preference Outputs according to the Schedule of Assessments ([Table 1](#)).

Figure 1: Study BA058-05-022 Study Design

[figure not shown]

Table 1: Schedule of Assessments

Procedure	Study Visit	1	2	Treatment Period			6
				3	4	5	
	Visit Day	Screening (-67 to -8)	Pre-Treatment (-7 to -1)	Day 1	Day 15	Day 29 / End of Treatment (EOT)	Day 36 (Follow-up)
Procedure	Visit Window (Days)	N/A	± 2	± 2	± 2	± 2	± 2
Informed consent		X					
Verification of entry criteria		X					
Physical examination ¹		X					
Review of medical history ²		X					
Symptom directed physical examination ¹			X	X	X	X	
Vital signs ³		X		X	X	X	
Weight measurement		X	X	X	X	X	
Height measurement ⁴		X					
ECG ⁵		X		X	X	X	
Urinalysis (dipstick) ⁶		X		X	X	X	
Chemistry blood collection ⁷		X		X	X	X	
Serum calcium, albumin, phosphorus ⁸				X	X	X	
Cyclic AMP ⁹				X	X	X	
24 hour urine collection (for calcium:creatinine and creatinine clearance) ¹⁰			X				
Hematology ⁷		X		X	X	X	
Coagulation (PT and PTT) blood collection		X					
PTH (intact)		X					
25-hydroxyvitamin D level		X					
1,25-dihydroxyvitamin D level		X					
Estradiol, FSH		X					
Serum pregnancy		X					
Thyroid stimulating hormone		X					
Urine Drug and Alcohol Test ¹¹		X		X			

Procedure	Study Visit	1	2	Treatment Period			6
				3	4	5	
	Visit Day	Screening (-67 to -8)	Pre-Treatment (-7 to -1)	Day 1	Day 15	Day 29 / End of Treatment (EOT)	Day 36 (Follow-up)
Procedure	Visit Window (Days)	N/A	± 2	± 2	± 2	± 2	± 2
Subject training on study drug administration, completion of subject diary and assessment of symptoms of local skin reactions ¹²				X			
Dispensing of calcium and vitamin D supplements			X	X	X		
Study drug administration ¹³				Every day between Visit 3 and Visit 5, inclusive			
Collect used abaloparatide-sMTS and swab for residual drug and swab residuals				X	X	X	
BMD of lumbar spine, total hip and femoral neck by DXA ¹⁴	X						
Investigator assessment of signs of local skin reaction ¹⁵				X	X	X	
Subject assessment of symptoms of local skin reaction ¹⁶				Every day between Visit 3 and Visit 5, inclusive			X ²³
Subject assessment of patch adhesion ¹⁷				Every day between Visit 3 and Visit 5, inclusive			
Subject assessment of pain ¹⁸				Every day between Visit 3 and Visit 5, inclusive			
Subject assessment of user errors				Every day between Visit 3 and Visit 5, inclusive			
Assessment of subject preferences for treatment attributes				X	X	X	
Assessment of subject convenience and satisfaction (TSQM9)					X	X	
Assessment of subject acceptability (5-point Likert scale)				X	X	X	
Subject diary review ¹⁹				X	X	X ²⁴	
Document AEs and concomitant medication ²⁰		After signing informed consent until follow up visit					
PK draw ²¹				X	X	X	
Serum marker of bone metabolism (s-PINP) ²²				X	X	X	
Drug supply / Drug re-supply				X	X		

Procedure	Study Visit	1	2	Treatment Period			6
				3	4	5	
	Visit Day	Screening (-67 to -8)	Pre-Treatment (-7 to -1)	Day 1	Day 15	Day 29 / End of Treatment (EOT)	Day 36 (Follow-up)
Visit Window (Days)	N/A	± 2	± 2	± 2	± 2	± 2	± 2
Drug Accountability					X	X	

1. A complete physical examination includes a review of the following systems: head/neck/thyroid, eyes/ears/nose/throat, respiratory, cardiovascular, lymph nodes, abdomen, skin, musculoskeletal, and neurological. Breast, anorectal, and genital examinations will be performed when medically indicated. After screening, any clinically significant abnormal findings from the symptom-directed physical examinations should be reported as AEs.
2. Including alcohol and tobacco use assessment.
3. Blood pressure, pulse rate, body temperature, and respiration rate are to be recorded predose at each study visit. Only blood pressure, pulse rate and respiration rate are to be recorded 1 hour after abaloparatide-sMTS application at each study visit during the treatment period. All blood pressure assessments will be orthostatic. Pulse rate will also be obtained at 15 minutes after abaloparatide-sMTS application at Day 1 (Visit 3), Day 15 (Visit 4) and Day 29 (Visit 5/EOT).
4. Height is to be measured at the screening visit/ Visit 1 in the standing position using a medical stadiometer.
5. During the Treatment Period, ECGs are to be performed predose after 5 minutes of rest and prior to any blood draw, and 1 hour after abaloparatide-sMTS application on Day 1 (Visit 3), Day 15 (Visit 4) and Day 29 (Visit 5/EOT).
6. All routine urinalysis will be performed on a sample freshly voided during the visit and sent to a local laboratory for microscopy if test is positive for micro-organisms via dipstick.
7. Blood draw for serum chemistry and hematology will be done during the Screening (Visit 1) and at predose on Day 1 (Visit 3), Day 15 (Visit 4) and Day 29 (Visit 5/EOT).
8. Blood draw for serum calcium, albumin and phosphorus will be done at predose and at 4 hours after abaloparatide-sMTS application on Day 1 (Visit 3), Day 15 (Visit 4) and Day 29 (Visit 5/EOT).
9. Blood draw for cAMP taken predose and at 30 minutes after abaloparatide-sMTS application on Day 1 (Visit 3), Day 15 (Visit 4) and Day 29 (Visit 5/EOT).
10. A 24 hour urine collection will start on Day -8 and complete on the day of the pre-treatment visit (Day -7).
11. All subjects will have a urine drug screen for drugs of abuse and alcohol performed on the Screening Period (Visit 1), and on Day 1 (Visit 3).
12. When necessary, re-training may be done post Day 1 / Visit 3.
13. Study drug is self-administered daily beginning Day 1 (Visit 3) through Day 29 (Visit 5/EOT), inclusive. On Days 1, 15, and 29, subject will self-administer abaloparatide-sMTS at the study site.
14. BMD measured by DXA at Screening visit if most recent DXA was done over 12 months prior to screening.
15. Investigators will perform an assessment of the application site at each clinic visit prior to application of abaloparatide-sMTS, 5 minutes after application (ie, immediately upon removal of the patch), and 1- hour following abaloparatide-sMTS application. Signs of local skin reactions will be assessed using a 4-point scale, as described in Section 6.6.2.1 of the protocol.

16. The subject will maintain a diary to record their assessment of symptoms of local skin reactions for 29 days beginning on Day 1 (Visit 3). The subject will evaluate the application site prior to study drug administration, 5 minutes after application (ie, immediately upon removal of abaloparatide-sMTS), and 1 hour after abaloparatide-sMTS application. Symptoms of local skin reactions will be assessed using a 4-point scale as described in Section 6.6.2.2 of the protocol.
17. Subject assessment of patch adhesion immediately prior to abaloparatide-sMTS removal on each day of the treatment period from Day 1 (Visit 3) to Day 29 (Visit 5/EOT).
18. An assessment of pain (separate from the pain question on the 4-point scale for local tolerance) will be done after sMTS application.
19. The Subject Diary will be reviewed by study personnel at each study visit to ensure subject compliance.
20. AEs and SAEs will be recorded on the case report forms starting from the signing of the informed consent until 7 days after the last dose of study medication. All treatment-related AEs will be followed until resolution or stabilization. Any SAEs that occur at any time after completion of the study, which are considered by the investigator to be related to study treatment, must be reported to the Sponsor or its designee.
21. Blood samples for measurement of plasma concentrations of abaloparatide will be taken at Day 1 (Visit 3), Day 15 (Visit 4) and on Day 29 (Visit 5/EOT). The pharmacokinetic measurements will be assessed predose and at 10 minutes, 20 minutes, 30 minutes, 1 hour, 1.5 hours, 2 hours, 3 hours and 4 hours after abaloparatide-sMTS application.
22. Blood samples for s-PINP taken within 1-hour prior to dosing on Day 1 (Visit 3), Day 15 (Visit 4) and Day 29 (Visit 5/EOT).
23. Assessed only for subjects with signs or symptoms of local skin reactions ongoing as of Day 29.
24. Subject will return diary to study site.

1.2.2 Randomization Methodology

This is a single arm study, and randomization is not used. i.e., not applicable.

1.2.3 Unblinding

This is an open-label study, and there is no blinding of study medication. i.e., not applicable.

1.2.4 Study Procedures

The schedule of assessments, as outlined in the study protocol, is provided in **Table 1**.

1.2.5 Study Endpoints

1.2.5.1 Primary Endpoint

The primary endpoint is the systemic exposure of the drug at Day 1, Day 15 and Day 29. Details for the analysis of the primary endpoint are provided in the Pharmacometric Analysis Plan (PAP).

1.2.5.2 Secondary Endpoints

Pharmacodynamic Endpoints

Pharmacodynamic endpoints include:

- Change, percent change from baseline, and ratio from baseline to Day 15 and Day 29 in s-PINP.
- Change and percent change in serum calcium (albumin-corrected) from baseline to each post-dose timepoint.
- Change and percent change in serum phosphorus from baseline to each post-dose timepoint.
- Change and percent change in cAMP from baseline to each post-dose timepoint.

Other Endpoints

Other endpoints include subject/investigator-reported outcomes:

- Investigator assessment of signs of local skin reaction using a 4-point scale at Day 1, Day 15 and Day 29
- Subject assessment of symptoms of local skin reaction using a 4-point scale from Day 1 through Day 29 as recorded in the subject diary
- Subject satisfaction and convenience of treatment as measured by Treatment Satisfaction Questionnaire for Medication (TSQM9) at Day 15 and Day 29
- Subject acceptability measurement (5-point Likert Scale) at Day 1, Day 15 and Day 29
- Subject preference for treatment attributes at Day 1, Day 15 and Day 29
- Daily measurement of patch adhesion as recorded in the subject diary
- Daily measurement of user errors as recorded in the subject diary

1.2.5.3 Safety and Tolerability Endpoints

Safety evaluations will be based on AEs, vital signs (orthostatic blood pressure, pulse rate, body temperature, and respiration rate), ECG, and laboratory tests (serum chemistry, hematology, coagulation, and urinalysis).

2 SUBJECT ANALYSIS POPULATIONS

2.1 Population Definitions

Three subject populations will be considered in the statistical analyses of this study.

Safety Population

The Safety Population is defined as all subjects who received at least 1 dose of study medication.

Pharmacokinetic Analysis Population

The PK Analysis Population will include all subjects in the Safety Population who have sufficient evaluable plasma concentrations to reliably estimate one or more PK parameters. Further details will be provided in the Pharmacometric Analysis Plan (PAP).

Bone Metabolism Population

The Bone Metabolism Population is defined as all subjects in the Safety population who have baseline and at least one post-baseline s-PINP.

The primary population for all safety analyses will be the Safety Population, and the primary population for PK analyses will be the Pharmacokinetic Analysis Population. The primary population for the analysis of the secondary endpoints (i.e., pharmacodynamic and other endpoints) will be the Safety Population, unless otherwise specified. The Bone Metabolism Population will be used for all analyses involving s-PINP.

2.2 Protocol Deviation and Protocol Violation

A protocol deviation is defined as a deviation from the protocol that does not impose added risk to the study data or the study subject.

A protocol violation is defined as a deviation from basic requirements of the study protocol, including inclusion and exclusion criteria, concomitant medication restrictions, or any protocol requirements that result in a significant added risk to the study subject or has an impact on the quality of the data collected or the outcome of the study.

Subjects with protocol deviations and/or protocol violations will be collected by the clinical trial vendor (PRA) using their Clinical Trial Management System (CTMS). The list of protocol deviations and protocol violations will be reviewed by the clinical team on a regular basis throughout the study. At the end of the study, a list of the protocol deviations/violations will be generated from the CTMS and included in the clinical study report (CSR).

3 GENERAL STATISTICAL METHODS

3.1 Sample Size Planned and Specified in the Protocol

This is a hypothesis generating study and the sample size is based on previous clinical trial experience without a formal power calculation.

3.2 General Methods

Analyses of the pharmacokinetic endpoints will be described in a separate Pharmacometric Analysis Plan (PAP).

For all summaries of pharmacodynamic and safety endpoints, continuous variables will be summarized with the following descriptive statistics: number of observations, (arithmetic) mean, standard deviation (SD), median, interquartile range (Q1 and Q3), minimum, and maximum. Categorical data will be summarized with frequencies for each category and corresponding percentages.

All data listings that contain an evaluation date will contain a relative study day. Screening, pre-treatment and on-treatment study days are numbered relative to the day of the first dose of study medication which is designated as Day 1. The preceding day is Day -1, the day before that is Day -2, etc.

In listings, data will be presented with the same precision as the original data. Derived data may be rounded to 1 decimal place greater than the original data for presentation purposes.

Frequency percentages will be presented with 1 decimal.

For all summaries, the mean and median will be presented to 1 decimal place greater than the original data, standard deviation (SD) to 2 greater than the original data, and the minimum and maximum will be presented to the same number of decimal places as the original data.

No statistical tests will be conducted on the pharmacodynamic and safety endpoints.

3.3 Computing Environment

All descriptive and statistical analyses will be performed using SAS statistical software Version 9.4, or later version. Medical history and AEs will be coded using the Medical Dictionary for Regulatory Activities (MedDRA), Version 22.0. Concomitant medications will be coded using the World Health Organization Drug Dictionary (WHO Drug Global March 2019 B3).

3.4 Baseline Definitions

Unless otherwise specified, the baseline value is defined as the last value obtained prior to the first dose of study medication.

3.5 Data Pooling

Not applicable since there is only one site involved in this study

3.6 Adjustments for Covariates

No adjustment for covariates will be made in any of the planned analyses for study endpoints.

3.7 Multiple Comparisons

Not applicable.

3.8 Subgroups

Not applicable.

3.9 Withdrawals, Dropouts, Loss to Follow-up

Data from subjects who do not complete the study, or who are lost to follow-up will be included in data listings and in summary tables, as appropriate.

3.10 Missing, Unused, and Spurious Data

Unless otherwise specified, there will be no imputation of pharmacodynamic and safety data.

In the event that incorrect data are discovered after database lock, the impact of such incorrect data will be assessed and a determination will be made as to whether the data need to be corrected in the database (and subsequently in the analysis). In cases where it is decided that the data need to be corrected, the decision will be documented and the documentation will be saved in the Trial Master File.

All available data will be included in data listings.

3.11 Visit Windows

Unless otherwise specified, data will not be analyzed using visit windows; instead, the nominal visit will be used.

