## 4.3.2. Handling of Subject Withdrawals or Terminations

If a subject is withdrawn or discontinued from the study, the reason for withdrawal from the study must be recorded in the source documents and on the case report form. All subjects withdrawn prior to completing the study should be encouraged to complete study procedures scheduled for the Visit 5 / end of treatment (EOT) (Day 29) visit as soon as possible. All AEs should be followed as described in Section 7. Subjects who discontinue or are withdrawn from the study will not be replaced. Whenever a subject is discontinued prematurely, the Sponsor and the Medical Monitor must be notified.

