## 4.7. Temporary Suspension of Treatment

Due to the short nature of the study, temporary suspension of treatment is not an option for the Investigator. Any subject that is deemed inappropriate for continuing treatment will be withdrawn from the study and the reason will be noted in the CRF.

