## 6.2. Study Schedule

This study is comprised of 5 clinic visits with either a sixth visit or telephone call for Follow-up. Study assessments are to be performed according to the SOA (Table 1). There is a  $\pm$  2-day window for each clinic visit.

The study will consist of a Screening (up to 2 months), a Pre-treatment Period (1 week), a Treatment Period (29 days) and a Follow-up Period (7 days). During the Treatment Period, subjects will have clinic visits for study-related protocol procedures at Day 1, Day 15 and Day 29. The Treatment Period of the study will be considered complete when the last subject completes the last clinic visit.

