4.6 Analyses of Secondary Endpoints

4.6.1 Percent change of s-PINP from baseline to Day 15 and Day 29

The actual values, change from baseline values, percentage change from baseline values, geometric mean, geometric mean (SE) of ratio (post-baseline value to baseline value) in s-PINP will be summarized descriptively by visit, together with the 90% CI.

4.6.2 Change and percent change in serum calcium (albumin-corrected) from baseline to each post-dose timepoint

The actual values, change from baseline values, and the percentage change from baseline values will be summarized using descriptive statistics by visit and timepoint. A scatter plot will be used to present the relationship between the change from baseline (on y-axis) and total released dose as defined in Section 4.7.7 (on x-axis) for each timepoint.

4.6.3 Change and percent change in serum phosphorus from baseline to each post-dose timepoint

The same analyses described in Section 4.6.2 will be used.

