9.3.3 Incomplete Dosing Information

Missing dose dates and/or times may be imputed using nominal dosing times. The imputation strategy will be discussed with Radius. All pharmacokinetic samples associated to a missing dosing date and/or time that cannot be imputed will be excluded from the analysis.

Subjects with a documented patch adherence issue will be reviewed by CSC and Radius for inclusion/exclusion from the descriptive statistics on a case-by-case basis.

In the case where subjects were dosed with abaloparatide-sMTS but discontinued from the study (early termination), the concentration data will be reported in the concentration tables and included in all summary statistics and PK analysis if sufficient concentration data are available to usefully contribute to the PK analysis.

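### An end-of-treatment assessment by a subject who stopped early would be summarised as Day 29, whatever the actual study day

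*SAP*

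**What the plan says.** - **Early withdrawals.** Protocol 4.3.2 says subjects withdrawn before completion should be "encouraged to complete study procedures scheduled for the Visit 5 / end of treatment (EOT) (Day 29) visit as soon as possible". They are not replaced. Protocol 4.7 rules out pausing treatment: "Any subject that is deemed inappropriate for continuing treatment will be withdrawn from the study".
- **Visit label.** The Schedule of Assessments (Table 1 in both the protocol and the SAP) has one Visit 5 column serving both Day 29 and end of treatment. There is no early-termination visit. Protocol 6.2 sets a ± "2-day window for each clinic visit", which governs scheduling and is not an analysis rule.
- **Analysis rule.** SAP 3.11 says that "data will not be analyzed using visit windows; instead, the nominal visit will be used", unless another section specifies otherwise. No section does so for early EOT data. SAP 3.9 puts non-completers' data into summary tables where appropriate, without saying which visit row.
- **s-PINP.** The Bone Metabolism Population (SAP 2.1) needs a baseline and one later value, so a subject whose only later value is an early EOT draw belongs to it. SAP 4.6.1 says the results "will be summarized descriptively by visit, together with the 90% CI".
- **Adherence split.** SAP 4.7.1 defines adherence at Day 15 and Day 29 by the median percent change in s-PINP, then describes TSQM-9 on either side of it. SAP 4.7.2 uses the same split for acceptability.
- **PK.** The Pharmacometric Analysis Plan (PAP), bound with the SAP, governs PK. Under PAP 9.3.3, concentrations from subjects who discontinue are "included in all summary statistics and PK analysis if sufficient concentration data are available" to contribute usefully. PAP 9.2.3 names PKDAY or VISIT as examples of the day factor and does not choose between them.

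**The concern.** The primary objective concerns self-administration over 29 days, and the Day 29 row is where a reader will look for the result at the end of that period. Because EOT and Day 29 share one visit label and the label decides the row, a subject who stopped after about a week would count as a Day 29 observation, possibly when already off drug.

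For a marker expected to build up with continued dosing, such as s-PINP, that mixes different exposures under one heading and moves the centre of the 90% CI. It also feeds the Day 29 median that separates adherent from non-adherent subjects, so below the median could partly mean stopped early.

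**Working it through.** **1. Planned numbers.** The protocol synopsis and PAP 7.3 give about 22 treated and at least 18 completing. There is no power calculation, effect size or SD to reproduce (protocol 8.5, SAP 3.1). The two figures imply at most 22 − 18 = 4 non-completers, and 4/22 = 18.2%.

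**2. Effect on a mean change.** Let k be the number of early EOT values among 22 in the Day 29 row. Let f be the early stoppers' mean change as a fraction of the completers' Day 29 mean change. The documents do not give f, so it is assumed.

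Row mean / completer mean = 1 − (k/22)(1 − f)

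| k | f = 0 | f = 0.25 | f = 0.5 | f = 0.75 | f = 1 | f = 1.25 |
|---|---|---|---|---|---|---|
| 1 | 0.955 | 0.966 | 0.977 | 0.989 | 1.000 | 1.011 |
| 2 | 0.909 | 0.932 | 0.955 | 0.977 | 1.000 | 1.023 |
| 4 | 0.818 | 0.864 | 0.909 | 0.955 | 1.000 | 1.045 |

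With k = 4 the pull toward zero is 18.2% at f = 0 and 9.1% at f = 0.5. It vanishes at f = 1 and reverses above that.

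**3. Geometric mean ratio.** With four early stoppers showing no change, the row ratio is R^(18/22). An assumed completer ratio R of 1.20 becomes 1.16, and 1.50 becomes 1.39.

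**4. Dependence on stopping day.** If the change is assumed linear from Day 1 to Day 29, f = (d − 1)/28 for an EOT visit on day d. Day 8 gives f = 7/28 = 0.25 and Day 22 gives 21/28 = 0.75. For an assumed completer change of +50%:
- Day 8: 48.3% with k = 1, 46.6% with k = 2, 43.2% with k = 4.
- Day 22: 49.4% with k = 1, 47.7% with k = 4.

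For an assumed +80% and Day 8, the row mean is 74.5% with k = 2 and 69.1% with k = 4.

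**5. Interval width.** Take four Day 8 stoppers and +50%, so the group means are 50 and 12.5. The 90% CI half-width, in percentage points, depends on the assumed within-group SD:

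| SD | 22 mixed values | 18 completers |
|---|---|---|
| 20 | 9.0 | 8.2 |
| 30 | 12.0 | 12.3 |
| 50 | 18.7 | 20.5 |

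The interval may be wider or narrower. In every case its centre is 50 − 43.2 = 6.8 points lower.

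**6. Median split.** With 22 distinct values, 11 lie on each side. If all four early stoppers fall below the median (assumed), they fill 4 of 11 places (36%), with 7 completers beside them. Completers alone would split 9 and 9, so two completers change group.

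**The case against.** Several points on the other side stand and limit the finding.

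- **Not every early stopper supplies a value.** Attendance is encouraged, not required. A subject who withdraws consent has no further assessments (protocol 6.7.1), and one lost to follow-up gives none. Four is therefore a ceiling on the planned numbers.
- **PK lies outside SAP 3.11.** A reader might infer that the primary endpoint is caught by the same rule. The documents do not support that. PAP 9.3.3 says early-termination concentrations may be used, but not that they become Day 29 values, and it also covers such a subject's valid Day 1 or Day 15 profiles. PAP 9.1.2 allows a profile to be excluded case by case after a missed dose. What remains is the undecided day factor in PAP 9.2.3.
- **TSQM-9 is restricted in the protocol.** Protocol 8.4.3 tabulates it for subjects who completed the study. SAP 4.7.1 does not repeat this, and SAP 5 does not list a change. That is an inconsistency to resolve, and it does not show that early stoppers will be included.
- **The flexible wording in SAP 3.9** leaves room for another treatment of these data. It names none, however, while SAP 3.11 states a positive rule. Settling the matter later would mean choosing with open-label results in view.
- **The study is descriptive.** There are no formal tests, and SAP 3.2 shows relative study day in listings, so an early EOT visit could be found there. The summary tables would not show it.

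**Conclusion.** The gap holds for s-PINP, acceptability and the Day 29 adherence split. The early-withdrawal instruction, the shared visit and the nominal-visit rule together place an early EOT value in the Day 29 row, and no passage prevents it.

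The share is at most 4 of 22 (18%), provided at least 18 subjects complete. For s-PINP, attenuation is plausible: up to about 18% of the mean change if early stoppers show none, and about 9% if they show half. This rests on assumed fractions between 0 and 1.

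A reader might infer that all Day 29 results are diluted and their variance inflated. The documents do not support either. For acceptability, satisfaction, local tolerance, cAMP, calcium and per-dose exposure they give no direction, and early stoppers could differ either way. The confidence interval can also narrow, as step 5 shows. The supportable statement is that shorter exposures are mixed into Day 29, with a likely direction only for s-PINP.

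**What to change.** - **SAP 3.11:** keep the Day 29 row for Visit 5 assessments made within Day 29 ± 2. Report earlier EOT assessments under a separate Early Termination label in summaries and listings, and retain them in AE and worst-value safety summaries. Do not move them into the Day 15 row unless the subject was still on daily dosing at that assessment. Otherwise an off-drug value could enter Day 15 and the mixing would only shift.
- **SAP 4.7.1 and 4.7.2:** base the Day 29 median split on the Day 29 row so defined.
- **PAP 9.2.3:** define the day factor the same way, so that an early-termination profile does not enter the Day 29 versus Day 1 contrast.
- **SAP 4.7.1, TSQM-9:** restore the protocol's completer restriction, or declare its removal in SAP 5.

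The cost is a few sentences across the SAP and PAP. Day 29 n falls by the number of early EOT visits, and no data are lost. The row then describes subjects who reached Day 29, which is itself a selected group, and the report should say so.
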